### 12.2.4 Serious Device Adverse Effects

For SAEs or suspected SAEs that are categorized by an Investigator as definitely, possibly, or probably related to the Amplifi System, the Medical Monitor will adjudicate whether the SAE or suspected SAEs is a SADE.

Investigators will review all reports of Amplifi System deficiencies, malfunctions, or unplanned stoppages and determine if an SAE or suspected SAE occurred. If an Investigator determines that an SAE or suspected SAE occurred, they will document the SAE or suspected SAE on the appropriate CRF. The Investigator will also document, in their opinion, the likelihood the SAE was related to the Amplifi System using the relational criteria summarized in **Section 12.2 Classification of Adverse Events** and the Medical Monitor will adjudicate with PI whether the SAE or suspected SAE is a SADE.

Investigators will follow all SADEs and suspected SADEs until they have resolved, have a stable level of sequelae, or, in the Investigator's opinion, are no longer clinically relevant.

### 12.2.5 Unanticipated Serious Adverse Device Effect

An unanticipated serious adverse device effect (USADE) is a SADE which, by its nature, incidence, severity, or outcome, has not been identified or fully identified during the Amplifi System risk analysis process and is not included or fully included in the Amplifi System risk analysis documents as a potential SADE.

For SAEs or suspected SAEs that are categorized by an Investigator as possibly, probably, or definitely related to the Amplifi System, Investigators will characterize whether the SAE or suspected SAE is definitely not, possibly, probably, or definitely a SADE. Investigators will document the characterization on the appropriate CRF. The Investigator's characterization of these events in the appropriate CRF(s) along with hospital source records will be reviewed and adjudicated by the Medical Monitor.

## Clinical Protocol FIH-3

Doc No: CLINP1837  
Revision: D  
DCO No: 25-009  
Effective Date: 02/06/25

Investigators will follow all USADEs and suspected USADEs until they have resolved, have a stable level of sequelae, or, in the Investigator's opinion, are no longer clinically relevant.

### 12.2.6 Potential Adverse Events and Serious Adverse Events

AEs and SAEs that may occur during the placement, operation, use, or removal of the Amplifi System, or the subsequent creation and use of an AVF made with a vein treated with the Amplifi System have been identified during the Amplifi System risk analysis process, included in the Amplifi System risk analysis documents, and are summarized here:

- death;
- vascular injury;
- bleeding;
- pneumothorax;
- air embolism;
- vascular thrombosis;
- thromboembolism;
- hemolysis;
- anemia;
- thrombocytopenia;
- Inflow Catheter and Distal Outflow Catheter dislodgement;
- Amplifi System component fracture or laceration;
- Inflow Catheter and Distal Outflow Catheter tunnel or skin exit site infection;
- Amplifi System thrombosis;
- Amplifi System component failure or replacement;
- unplanned re-hospitalization or prolonged hospitalization;
- unplanned surgery or interventional procedure;
- AVF bleeding or thrombosis;
- AVF infection;
- ipsilateral vascular access steal syndrome after creation of an AVF;
- AVF aneurysm or pseudoaneurysm formation;
- allergic reaction; and
- drug toxicity.

AEs and SAEs that may occur during the placement, operation, use, or removal of the Amplifi System, or the subsequent creation and use of an AVF made with a vein treated with the Amplifi System may be related to:

- testing required prior to Amplifi System treatment;
- the Amplifi System placement procedure;
- the operation and use of the Amplifi System;
- procedures where the Amplifi System is evaluated, such as venography;
- the Amplifi System removal procedure;
- surgery to create a Study AVF; and

- cannulation of a Study AVF.

AEs and SAEs that may occur during the placement, operation, use, or removal of the Amplifi System, or the subsequent creation and use of an AVF made with a vein treated with the Amplifi System may or may not be related to the Amplifi System, based on the relational criteria summarized in **Section 12.2 Classification of Adverse Events**.

## **12.2 Classification of Adverse Events**

### **12.2. Grading of AEs**

Investigators will grade adverse events using the following scale.

- *Mild*: easily tolerated
- *Moderate*: sufficiently discomforting to interfere with daily activities
- *Severe*: prevents normal daily activities

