## **8.4 Laboratory Assessments**

- A routine chemistry panel will be evaluated at baseline, at day 1 prior to Amplifi System placement, and at the end of Amplifi System treatment.
- A complete blood count (CBC) will be evaluated at baseline, on day 1 prior to Amplifi System placement, daily during the Amplifi System treatment period, at the end of Amplifi System treatment after Amplifi System removal, and 1, 2 weeks and 6 weeks after Study AVF creation. The baseline CBC results will be used to assess eligibility, the daily testing during the Amplifi System treatment period and the testing 1, 2 weeks and 6 weeks after Study AVF creation will be used to assess for hemolysis and anemia.
- PFH and LDH will be evaluated at baseline, on day 1 prior to Amplifi System placement, daily during the Amplifi System treatment period, at the end of Amplifi System treatment period after Amplifi System removal, and 1, 2 weeks and 6 weeks after Study AVF creation to assess for hemolysis.
- ACT will be evaluated during Amplifi System placement and removal, as per the Amplifi IFU, and during AVF creation, as per Standard of Care.

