## **12.1 Definitions**

### **12.1.1 Adverse Events**

An adverse event (AE) is defined as any untoward medical occurrence, unintended disease or injury, or untoward clinical sign or abnormal lab finding in a Subject, regardless of whether the AE was related to the Amplifi System or Study. Stable, chronic, pre-existing conditions will not be categorized as AEs. However, worsening of these conditions occurring during the Study Period may be categorized as AEs.

Investigators will categorize AEs or suspected AEs as unrelated, possibly related, probably related, or definitely related to the Amplifi System using the relational criteria summarized in **Section 12.2 Classification of Adverse Events**.

Investigators will document all AEs and suspected AEs occurring during the Study Period on the appropriate CRF regardless of whether the AE or suspected AE was related to the Amplifi System or Study. Documentation of the AE or suspected AE will include the characterization of the likelihood the AE was related to the Amplifi System.

Investigators will follow all AEs or suspected AEs until they have resolved, have a stable level of sequelae or, in the Investigator's opinion, are no longer clinically relevant.

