#### **14.2.3 Analysis of Safety Measures**

All safety data for the Subjects will be summarized descriptively and the number of AEs, ADEs, SAEs, and SADEs will be reported as a single group. The AEs, ADEs, SAEs, and SADEs will be grouped by type, and the number and percentage of Subjects experiencing each type will be reported as a single group. An assessment of the severity and causative relation to Amplifi System placement, treatment, and removal, and Study AVF creation and use for each AE, ADE, SAE, and SADE will be reported.

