- providing Sponsor with the Study documents and records necessary for a complete review of the work related to the Study at the Site by Investigator;
- meeting all Study reporting obligations, including:
  - reporting actual or suspected Amplifi System deficiencies, malfunctions, or

- unplanned stoppages to Sponsor, as specified in **Section 12.10 Reporting**;
- reporting actual or suspected AEs, SAEs, SADEs, and USADEs to Sponsor, as specified in **Section 12.10 Reporting** and submitting accurate, complete, and timely adverse event reports to Sponsor; and
- submitting all other reports to the Sponsor that are required,
- grading adverse events using the scale summarized in **Section 12.2 Classification of Adverse Events**;
- determining whether, in the opinion of the Investigator, an adverse event is related to the Amplifi System or Study procedures or surgeries using the criteria summarized in **Section 12.2 Classification of Adverse Events**;
- determining whether, in the opinion of the Investigator, an Amplifi System-related complication is an Amplifi System-related major complication;
- following all known and suspected AEs, ADEs, SADEs, and USADEs until they have resolved, have a stable level of sequelae, or, in the Investigator's opinion, are no longer clinically relevant;
- understanding and accepting the obligations of continuing review by their local EC while conducting the Study, including notifying their local EC of any changes to the Protocol per their local EC requirements, and submitting required reports to their local EC;
- reporting deviations from the Protocol to the Sponsor, as specified in **Section 10.9 Protocol Deviations and Investigator and Site Suspension and Termination**;
- notifying their local EC of Protocol deviations in accordance with their local EC requirements;
- reporting known and suspected AEs, SAEs, SADEs, and USADEs to their local EC in accordance with their local EC requirements;
- understanding and complying with all applicable local, regional, and national regulatory requirements while conducting the Study;
- communicating SAE, SADE, and USADE information and reporting all SAEs, SADEs, and USADEs to the appropriate regulatory agencies and bodies in accordance with relevant local, regional, and national regulatory requirements;
- recording the reason for withdrawal in source documentation and on the appropriate CRF for Subjects that withdraw from the Study;

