## Clinical Protocol

### FIH-3

Doc No: CLINP1837  
Revision: D  
DCO No: 25-009  
Effective Date: 02/06/25

system during the placement, operation, use, or removal of the Amplifi System that is not due to a cause other than the placement, operation, use, or removal of the Amplifi System; wherein the air embolism is documented by imaging and:

- results in air embolism-related hypotension, arrhythmia, hemodynamic instability, paradoxical embolization, myocardial infarction, stroke, mesenteric ischemia, or death;
- requires a procedure or surgery to remove the air that forms after air embolism; or
- requires a thrombectomy procedure or surgery, thrombolytic therapy, or long-term anticoagulation to remove thrombus that forms after air embolism.
- *Amplifi System-related major thrombosis* is defined as the formation of thrombus in an artery, vein, or the right atrium due to the placement, operation, use, or removal of the Amplifi System, wherein the thrombosis is documented by imaging and the Subject requires a thrombectomy procedure or surgery, thrombolytic therapy, or long-term anticoagulation; not inclusive of a thrombectomy procedure or surgery that occurs during the creation of the Subject AVF.
- *Amplifi System-related major thromboembolism* is defined as thromboembolism in the arterial or venous system due to the placement, operation, use, or removal of the Amplifi System, wherein the thromboembolism is documented by imaging and the Subject requires a thrombectomy procedure or surgery, thrombolytic therapy, or long-term anticoagulation; not inclusive of a thrombectomy procedure or surgery that occurs during the creation of the Subject AVF.
- *Amplifi System-related major hemolysis* is defined as hemolysis documented by laboratory testing during the Amplifi System treatment period that is not due to a cause other than the placement, operation, use, or removal of the Amplifi System, and requires blood transfusion and/or results in thrombotic events, multiple organ failure and mortality.
- *Amplifi System-related major thrombocytopenia* is defined as a platelet level of  $\leq 51,000$  per microliter during the Amplifi System treatment period that is not due to a cause other than the placement, operation, use, and removal of the Amplifi System, and requires transfusion.

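### The only AE severity scale ignores treatment given and laboratory or imaging findings, so a symptom-free event that needed treatment can be reported as Mild

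*Protocol*

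**What the plan says.** Section 12.2 (Grading of AEs) opens with "Investigators will grade adverse events using the following scale". Mild means the event is easily tolerated. Moderate means it is "sufficiently discomforting to interfere with daily activities". Severe means it prevents normal daily activities. Section 15.2 makes Investigators responsible for "grading adverse events using the scale summarized in" Section 12.2, and no other severity scale appears in the protocol.

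The events to be graded are broader than symptoms. Section 12.1.1 defines an AE as "any untoward medical occurrence, unintended disease or injury, or untoward clinical sign or abnormal lab finding in a Subject". Under Section 8.4, CBC is measured daily during treatment and again at 1, 2 and 6 weeks after AVF creation. These results "will be used to assess for hemolysis and anemia"; PFH and LDH are added to look for hemolysis. Thrombus is sought by ultrasound and venography after a prolonged Pump stoppage (Sections 8.1.2 and 8.5.3) and by venography at the end of treatment (Section 8.5.5).

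The grade is a reported result. Section 14.2.3 promises "An assessment of the severity and causative relation to Amplifi System placement, treatment, and removal", and also to AVF creation and use, for each AE, ADE, SAE and SADE.

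**The concern.** The protocol goes looking for harms that a Subject may not feel, then grades them only by what the Subject feels or can do. A finding serious enough to need transfusion, anticoagulation or thrombectomy meets no stated condition for Moderate or Severe if it causes no discomfort and leaves daily activities undisturbed. Mild is the only level whose wording it fits.

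At stake is the severity summary in Section 14.2.3 and any statement drawn from it. The safety analysis is descriptive, and Section 4.1 asks only that major complications stay within an acceptable range, so readers may lean on such a summary. A later analysis plan cannot easily repair this. Grades are assigned at the site under the protocol's definitions, and the analysis receives them as given.

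**Working it through.** No arithmetic applies. The check is to run symptom-free but treated events through each classification the protocol defines.

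1. **Cephalic vein thrombus after a Pump stoppage, removed during AVF creation.** Section 7.5 foresees this: ultrasound looks for thrombus, and the Investigator may go on to AVF creation and clear the vein, with mechanical thrombectomy given as an example.
   - *Grade (12.2):* without discomfort or loss of activity, Mild is open.
   - *Major thrombosis (Appendix 1):* the definition reads "wherein the thrombosis is documented by imaging and the Subject requires a thrombectomy procedure or surgery, thrombolytic therapy, or long-term anticoagulation", but then excludes a thrombectomy done during creation of the AVF. If that is the only treatment, the event falls outside the definition.
   - *SAE (12.2.3):* an intervention counts only if it prevents a life-threatening illness or injury, or permanent disability. Otherwise another criterion must apply, such as prolonged hospitalization or joint judgement by the Investigator and the Medical Monitor.
   - *Result:* the event can be neither major nor serious, and the one remaining measure of its clinical weight can read Mild.

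2. **Platelets at or below 51,000 per microliter, with transfusion and no symptoms.**
   - *Grade:* Mild is open.
   - *Major thrombocytopenia (Appendix 1):* met if the fall "is not due to a cause other than the placement, operation, use, and removal of the Amplifi System, and requires transfusion".
   - *Result:* one event can be both major and Mild. It still counts in the rate of major device-related events.

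3. **Imaged venous or right atrial thrombus due to the device, with long-term anticoagulation and no symptoms.**
   - *Grade:* Mild is open.
   - *Major thrombosis:* met.
   - *Result:* as in case 2.

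4. **Fatal or life-threatening event.**
   - *Grade:* Severe is the top level.
   - *SAE:* met directly, since death and threat to life are listed criteria. Section 14.2.3 reports SAEs by type, with the number and percentage of Subjects.
   - *Result:* the event is fully visible without a fourth level.

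Case 1 is therefore where the grade matters most. In cases 2 and 3 the grade is inconsistent with the major definition, but the event is not lost. Case 4 shows no gap.

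**The case against.** The strongest reply is that little depends on the grade. Device-related events such as cases 2 and 3 count in the rate of major device-related events whatever their grade. The thrombus in case 1 is recorded in the eCRF (Section 7.5) and, after a prolonged stoppage, on the ultrasound and venography forms (Sections 8.1.2 and 8.5.3). The stoppage is itself a technical performance measure. If the Investigator records an AE and rates it at least possibly related, the Medical Monitor adjudicates it as an ADE. The Investigator and Medical Monitor together may also declare a related complication major. Case 1 escapes *major thrombosis* because of the exclusion in Appendix 1, not because of the grade. All of this stands, and it limits the point to the severity output.

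It is also true that Mild is permitted rather than required. An Investigator may judge that an event needing transfusion is not easily tolerated. Nothing in Section 12.2 asks for that judgement, however, so the grade depends on individual reading.

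A reader might infer three stronger points, none of which the document supports:

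- *That the lack of a fatal level is a defect.* Severity and seriousness may properly be separate scales. Section 12.2.3 captures death and threat to life, and with at most ten Subjects a death could not be hidden by sharing a grade.
- *That the earlier study's events were graded too low,* because Section 3.2.3 describes none as worse than mild while Pumps were being replaced. The earlier scale is not stated, and the thrombus described was in the Pump's bearing gap, which is a device finding and not a graded patient harm.
- *That counting the laboratory and imaging items among the potential events in Section 12.2.6 measures the problem.* Such a count says nothing about how often Mild would be chosen, since those events can also cause symptoms.

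**Conclusion.** The point holds in a limited form. Section 12.2 contains the only severity scale, Investigators are bound to it, and it has no criterion for treatment required or for laboratory and imaging findings. A symptom-free AE that needed treatment can therefore be reported as Mild, which makes the severity output of Section 14.2.3 look more favourable than the events warrant. The main safety rate, the SAE classification and the AE-by-type tables are unaffected.

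The size cannot be given as a number, because the document states no frequency for such events. The conclusion assumes that the Investigator records the finding as an AE and grades by the wording of the scale. Case 1 further assumes that the thrombectomy takes place during AVF creation, that no thrombolysis or long-term anticoagulation is needed, and that no other SAE or major criterion applies. This is an optional improvement, worth making because it costs so little.

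**What to change.** Amend the three definitions in Section 12.2 themselves. Laying a separate rule over them would clash with the discomfort wording of Moderate. For example:

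- *Mild:* easily tolerated and requiring no medical or procedural treatment.
- *Moderate:* "sufficiently discomforting to interfere with daily activities", or requiring medical or procedural treatment (for example transfusion, anticoagulation, thrombolysis, or thrombectomy including at AVF creation), whether or not the Subject has symptoms.
- *Severe:* prevents normal daily activities, or is life-threatening or fatal.

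It would help to add that the treatment meant is treatment given for the event, not anticoagulation already in use during Amplifi treatment.

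The cost is a change to three lines of text, made before enrolment, and a brief note in site training. The three levels stay, so the severity field needs no new option. The blood tests, ultrasound, venography, medication records and procedure records are already in Table 3, so no new test or visit is needed. Whether the AE form already records treatment given is not shown. The downside is a somewhat less favourable severity table and possibly less comparability with the earlier first-in-human summary, which matters because Section 4.1 aims at outcomes similar to those studies.

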#### **12.2.2 Relational Criteria**

Investigators will document their opinion of the likelihood of the relationship of all adverse events to the Amplifi System using the criteria summarized below:

- *Unrelated*: a temporal relationship between the adverse event and the placement, use, or removal of the Amplifi System is not clear, or there is evidence of potential alternative causes for the adverse event such as concurrent medication or illness
- *Possibly related*: a temporal relationship between the adverse event and the placement, use, or removal of the Amplifi System is not clear and potential alternative causes for the adverse event such as concurrent medication or illness are possible
- *Probably related*: a temporal relationship between the adverse event and the placement, use, or removal of the Amplifi System is clear and potential alternative causes for the adverse event such as concurrent medication or illness are possible but unlikely
- *Definitely related*: a temporal relationship between the adverse event and the placement, use, or removal of the Amplifi System is clear and no potential alternative causes for the adverse event such as concurrent medication or illness are possible

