### **12.2.2 Device Adverse Events**

For AEs or suspected AEs that are categorized by an Investigator as definitely, possibly, or probably related to the Amplifi System, the Medical Monitor will adjudicate whether the AE or suspected AE is an ADE.

Investigators will review all reports of Amplifi System deficiencies, malfunctions, or unplanned stoppages and determine if an AE occurred during the reported event. If an Investigator determines that an AE or possible AE occurred, they will document the AE or possible AE on the appropriate CRF. The Investigator will also document, in their opinion, the likelihood the AE or possible AE was related to the Amplifi System using the relational criteria summarized in **Section 12.2 Classification of Adverse Events**.

Mild-moderate hand, wrist, arm, neck, or face swelling that resolves within 7 days after the end of the Amplifi System treatment period will not be categorized as an AE.

Investigators will follow all ADEs or suspected ADEs until they have resolved, have a stable level of sequelae or, in the Investigator's opinion, are no longer clinically relevant.

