## **12.3 Amplifi System Unplanned Stoppages, Malfunctions, and Potential Device Deficiencies**

All Amplifi System unplanned stoppages, including Pump stoppages, that occur and are observed during the Study, whether they are associated with an AE, ADE, SAE, SADE, or USADE, shall be documented by the Investigator and other Site Personnel by submitting a completed CRF in the Study EDC System.

All Amplifi System malfunctions and deficiencies that are related to the identity, quality, durability, reliability, safety, or performance of the Amplifi System that occur and are observed during the Study, whether they are associated with an AE, ADE, SAE, SADE, or USADE, shall

be documented by the Investigator and other Site Personnel by submitting a completed CRF in the Study EDC System. The Medical Monitor shall adjudicate device relatedness in accordance with protocol definitions.

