### **12.10.3 Reporting of SAEs**

Investigators will report SAEs or suspected SAEs to the Sponsor (or Sponsor delegate) as soon as possible, preferably within 24 hours, but no later than two (2) working days of the Investigator or Site Personnel becoming aware of an SAE or suspected SAE, by:

- calling Sponsor;
- emailing Sponsor;
- submitting a completed CRF through the Study EDC System, including documentation of the call and email to Sponsor or Sponsor delegate;

Investigators will report SAEs or suspected SAEs regardless of whether they are related to the Amplifi System or Study.

After notifying Sponsor or (Sponsor delegate) and Medical Monitor of an SAE or suspected SAE, Investigators will provide a written report of the SAE or suspected SAE to Sponsor within five (5) working days of the SAE or suspected SAE through the Study EDC System. Investigators will also transmit the written report to the Medical Monitor in accordance with the charter.

Investigators will report SAEs or suspected SAEs that, in their opinion, possibly related, probably related, or definitely related to the Amplifi System to the Medical Monitor for adjudication as SADEs through the Study EDC System, using the relational criteria summarized in **Section 12.3**.

Investigators will report SAEs or suspected SAEs to the Central EC, in accordance

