### 12.10.5 Reporting of USADEs

Investigators will report SAEs or suspected SAEs that are characterized by the Investigator as possibly, probably, or definitely related to the Amplifi System, and also characterized as possibly, probably, or definitely a SADE, to Sponsor (or Sponsor delegate) as soon as possible, preferably within 24 hours, but no later than two (2) working days after Investigator or other Site Personnel becoming aware of a USADE or suspected USADE, by:

- calling Sponsor;
- emailing Sponsor;
- submitting a completed CRF through the Study EDC System, including documentation of the call and email to Sponsor; and

After reporting a USADE or suspected USADE to Sponsor, Investigators will provide a written report about the USADE or suspected USADE to Sponsor within five (5) working days after Investigator or other Site Personnel becoming aware of the USADE or suspected USADE.

With Sponsor communication, Investigators will also report USADEs or suspected USADEs to the Central EC, in accordance with the EC requirements.

Sponsor will report all USADEs and communicate relevant USADE information to the appropriate regulatory agencies and bodies in accordance with relevant local, regional, and national regulatory requirements.

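### As worded, every event that meets 'possibly related' also meets 'unrelated', and required adjudication turns on which of the two the investigator picks

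*Protocol*

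**What the plan says.** **The scale.** Section 12.2.2 (Relational Criteria) has four levels. An event is *unrelated* if its temporal link to the device "is not clear, or there is evidence of potential alternative causes for the adverse event such as concurrent medication or illness". It is *possibly related* if that link "is not clear and potential alternative causes for the adverse event such as concurrent medication or illness are possible". *Probably related* needs clear timing and another cause that is possible but unlikely. *Definitely related* needs clear timing and no other possible cause. Section 15.2 gives the rating to the investigator.

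**What the rating triggers.**
- Section 12.2.2 (Device Adverse Events), for AEs: those "categorized by an Investigator as definitely, possibly, or probably related to the Amplifi System, the Medical Monitor will adjudicate" as adverse device effects (ADEs).
- Section 12.2.4, first paragraph, sets the same condition for serious adverse device effects (SADEs): "For SAEs or suspected SAEs that are categorized by an Investigator as definitely, possibly, or probably related to the Amplifi System".
- Section 12.2.5 sends SAEs rated possibly related or higher for characterisation and Medical Monitor review.
- Section 12.10.3 routes SAEs that the investigator thinks "possibly related, probably related, or definitely related to the Amplifi System to the Medical Monitor for adjudication as SADEs".
- Section 12.10.5 limits expedited reporting of unanticipated effects (USADEs) to SAEs "characterized by the Investigator as possibly, probably, or definitely related to the Amplifi System, and also characterized as possibly, probably, or definitely a SADE".

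**The exception.** For SAEs found when stoppages, malfunctions or deficiencies are reviewed, Section 12.2.4, second paragraph, says that "the Medical Monitor will adjudicate with PI whether the SAE or suspected SAE is a SADE" and states no minimum rating. Section 12.3 adds, for malfunctions and deficiencies: "The Medical Monitor shall adjudicate device relatedness in accordance with protocol definitions".

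**Where relatedness is counted.** Section 4.5 lists the rate of Major Device-Related Adverse Events (MDRAE) as one of two safety measures. Section 14.2.3 reports ADE and SADE numbers beside those for AEs and SAEs.

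**The concern.** The two lowest levels of a causality scale should separate events in which a device role can be dismissed from those in which it cannot. Here they do not: unclear timing alone is enough for *unrelated*, and unclear timing is also a required part of *possibly related*. Two investigators who apply the text correctly to the same event can record different answers.

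The difference matters because the boundary between these two levels is also the trigger for adjudication. If the lower rating is chosen, nothing in the protocol obliges anyone to re-examine it, apart from the serious stoppage-linked events. What is at stake is the set of counts that depend on attribution: ADEs, SADEs, and those parts of the MDRAE whose only causal test is the label. The stated safety objective (Section 4.1) is to confirm that major complications lie in an acceptable range, and with at most ten subjects a single attribution changes how that reads.

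**Working it through.** The protocol states no figure on this point to reproduce. The check is logical, followed by a short interval calculation.

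**Step 1. Enumerate the scale.** Inputs are the four definitions in Section 12.2.2 (Relational Criteria). Each event has timing (clear or not), another cause (none; possible but unlikely; possible and not unlikely) and evidence for that cause (yes or no).

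| Timing | Other cause | Evidence of it | Levels met |
|---|---|---|---|
| clear | none | – | definitely |
| clear | unlikely | no | probably |
| clear | unlikely | yes | probably **and** unrelated |
| clear | not unlikely | no | **none** |
| clear | not unlikely | yes | unrelated |
| not clear | none | – | unrelated |
| not clear | unlikely | no | possibly **and** unrelated |
| not clear | unlikely | yes | possibly **and** unrelated |
| not clear | not unlikely | no | possibly **and** unrelated |
| not clear | not unlikely | yes | possibly **and** unrelated |

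All 4 of the 4 combinations that meet *possibly related* also meet *unrelated*. The reason is general: if U = (timing not clear OR evidence of another cause) and P = (timing not clear AND another cause possible), then P implies its first condition, which implies U. One combination fits no level. One of the two *probably related* combinations also meets *unrelated*, if evidence for an unlikely cause is allowed.

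**Step 2. Follow an event rated unrelated.** Sections 12.2.2 (Device Adverse Events), 12.2.4 first paragraph, 12.2.5, 12.10.3 and 12.10.5 all start at *possibly related*, so none of them sends the event to adjudication or USADE reporting. The second paragraph of 12.2.4 does, but only for SAEs found on review of stoppages, malfunctions or deficiencies. For a non-serious AE found on such a review, the Device Adverse Events section has the investigator record a likelihood and does not require adjudication whatever the rating. Section 12.3 concerns malfunctions and deficiencies and does not clearly extend to the associated AE.

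**Step 3. See which MDRAE components depend on the label.** From Appendix 1:
- Death has no separate definition, major bleeding is defined by clinical criteria, and local infection by site and signs. None has a causal test in its body, so attribution rests on the label, or in local infection's case on its place in a list of system-related events.
- Pneumothorax, air embolism, hemolysis and thrombocytopenia (4 components) carry a test that rules out other causes.
- Thrombosis and thromboembolism (2 components) must be due to the device.
- Hospitalization, surgery and interventional procedure must be due to a system-related complication, which is itself defined by being related to the device.

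The protocol does not say how any of these tests maps to the four-level scale. A *probably related* hemolysis, for example, has another possible cause by definition, and it is not stated whether it passes a test that rules out other causes. The catch-all component needs the investigator and the Medical Monitor in Section 4.5, but the investigator and a CEC in Appendix 1.

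**Step 4. Size of one reclassification.** Inputs: n = 10, the maximum in Section 14.1, and one subject whose only major event is in doubt. Exact (Clopper-Pearson) 95% limits:
- 0/10: lower 0; upper 1 − 0.025^(1/10) = 1 − 0.6915 = 30.8%.
- 1/10: lower 1 − 0.975^(1/10) = 0.3%; upper is the p that solves (1−p)^10 + 10p(1−p)^9 = 0.025, which is 44.5%.

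The point estimate moves by 100/10 = 10 percentage points. Enrolment is a ceiling, so at an assumed n = 8 or n = 5 the move is 12.5 or 20 points.

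**The case against.** The best reply is that the consequence is narrower than the drafting error suggests, and much of that stands.

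- **Events are not hidden.** A reader might infer that a major event could vanish from the safety report. The documents do not support that. Section 14.2.3 tabulates all AEs and SAEs with attribution, Section 12.10.3 sends written SAE reports to the Medical Monitor, the safety board monitors overall safety (Section 12.0), and the sponsor reviews all AE and SAE reports (Section 15.1). What remains is that none of these provisions requires an *unrelated* rating to be re-adjudicated. The Medical Monitor's charter is cited but not shown, and it may add such a rule.
- **The scale does not visibly govern the whole MDRAE.** A reader might infer that every component can be lost this way. Most have their own causal wording, and four are tied to device use or the treatment period, which leaves little room for unclear timing. The claim is safe only for the components with no causal test of their own.
- **Investigators use judgement.** The scale is ordered and asks for an opinion on likelihood, so few would work through it as formal logic. On that view the combination that fits no level is a small drafting gap. The full overlap of two adjacent levels, with adjudication hanging on the boundary, is more than that.
- **The size is hypothetical.** The study is descriptive and unpowered, and it sets no numerical MDRAE threshold. The 0/10 versus 1/10 contrast shows what one event is worth, not what will happen.

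**Conclusion.** The scale is wrong as written. *Possibly related* has no case of its own, no tie-break is given, and one combination has no category. Because required adjudication and USADE reporting start at *possibly related*, a rating that complies with the protocol can keep a doubtful event out of the ADE and SADE counts. It can also keep it out of the MDRAE for death, major bleeding and local infection. The clear exception is SAEs found on review of stoppages, malfunctions or deficiencies.

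The size is at most illustrative: one subject is 10 percentage points at n = 10. It assumes that the subject has no other counted event, that the event would have been judged device-related on adjudication, and that the unseen charter does not already close the gap. The documents do not say how often timing or cause would be in doubt, and unclear timing may be uncommon during inpatient treatment. Nor do they support the stronger inference that every *possibly related* event ought to count in the MDRAE: no threshold is stated, and reasonable statisticians differ on where to set it. The protocol needs to state one. The point should be fixed before enrolment relies on the scale.

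**What to change.** 1. **Reword the scale in Section 12.2.2 (Relational Criteria) so that exactly one level applies.** Use *unrelated* only when a device relationship can reasonably be excluded, and consider it first. Use *possibly related* when it cannot be excluded and either timing is not clear or another cause is possible and not unlikely. Keep *probably* and *definitely* as they are for the remaining events. Once *unrelated* is ruled out, unclear timing gives *possibly*; clear timing gives *possibly*, *probably* or *definitely* according to whether another cause is not unlikely, unlikely or absent. No case overlaps or is left over.
2. **Remove the rating as the trigger.** Have the existing Medical Monitor adjudicate relatedness for all SAEs and all candidate MDRAE events, whatever the investigator recorded, and align the charter.
3. **State one rule** for how the adjudicated rating determines system-relatedness in the MDRAE, and reconcile the causal wording of the Appendix 1 components with it. The threshold is the sponsor's choice.
4. **Reconcile the catch-all component**, which names the Medical Monitor in Section 4.5 and a CEC in Appendix 1.

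The cost is protocol wording, a possible charter revision and a few more adjudications in at most ten subjects. The MDRAE rate may come out less favourable. No new data need be collected.
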